Process to Document Consent in Writing Consents are included with this submission.

IRB Study Number: 20210641
Version #4, Date: October 26, 2021

25) Authorization for Use and Disclosure of Protected Health Information (HIPAA)

If the research team will access patient medical records or other identifiable health information for this research, you must obtain a waiver of the requirement for written authorization from the patients to access their medical records.

Type of Request:

Waiver of Authorization for access to medical record for subject identification/recruitment.

Waiver of Authorization for access to medical record to obtain data for the research.

Confirm that you will destroy the Protected Health Information (PHI) you and/or your Study Team acquire receive from JHS and/or UHealth at the earliest opportunity.

I confirm

Confirm that the Protected Health Inform (PHI) you acquire from JHS and/or UHealth will not be re-used or disclosed to any other person or entity, except as required by law or for authorized oversight of the research study or for other research for which the use or disclosure of PHI is permissible.

I confirm

If you are collecting health information from JHS under a waiver of authorization, you must read the paragraph below and sign the signature block to indicate your agreement:

Not applicable. This research will not collect data from JHS record under a waiver of authorization

Notwithstanding the preceding “I confirm” statements above, I agree that neither I nor any member of the study team listed on the IRB submission for this Protocol shall ever re-use or re-disclose any of the information acquired from Jackson Health System in any format, whether **identifiable or de-identified**, to any individual or entity without first obtaining written permission from Jackson Health System, even if such re-use or re-disclosure is permissible by law (e.g., HIPAA).

PI Signature

Date

26) Drugs: Pfizer COVID-19 and Janssen COVID-19 Vaccines

Both vaccines will be provided by the Jackson Health System through the Department of Health.

IRB Study Number: 20210641
Version #4, Date: October 26, 2021

EMERGENCY USE AUTHORIZATION (EUA) OF THE PFIZER-BIONTECH COVID-19 VACCINE TO PREVENT CORONAVIRUS DISEASE 2019 (COVID-19)

The U.S. Food and Drug Administration (FDA) has issued an Emergency Use Authorization (EUA) to permit the emergency use of the unapproved product, **Pfizer-BioNTech COVID-19 Vaccine**, for active immunization to prevent COVID-19 in individuals 12 years of age and older.

The Pfizer-BioNTech COVID-19 Vaccine is a suspension for intramuscular injection administered as a series of two doses (0.3 mL each) 3 weeks apart.

The FDA has authorized the emergency use of the Janssen COVID-19 Vaccine to prevent COVID-19 in individuals 18 years of age and older under an Emergency Use Authorization (EUA).

The Janssen COVID-19 Vaccine is administered as a single dose, into the muscle
Safety Reporting / AE / SAE Definition:

For adverse events (AEs) not included in the protocol defined grading system, the following guidelines will be used to describe severity.

- **Mild** – Events require minimal or no treatment and do not interfere with the participant's daily activities.
- **Moderate** – Events result in a low level of inconvenience or concern with the therapeutic measures. Moderate events may cause some interference with functioning.
- **Severe** – Events interrupt a participant's usual daily activity and may require systemic drug therapy or other treatment. Severe events are usually potentially life-threatening or incapacitating. Of note, the term "severe" does not necessarily equate to "serious".

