Blood samples will be obtained from all patients at the time of enrollment (Day 1) and day 28 to test IgG and IgM against SARS-CoV-2 spike protein.

IRB Study Number: 20210641
Version #4, Date: October 26, 2021

At month 6, 50 optional patients will join to participate in the sub-study which will consist of blood sample collection to measure long term immunogenicity (IgG and IgM).

5) Sample Size calculation

The primary outcome of this study is IgG positivity after 28 (21-35) days of the booster dose of the either vaccine. This IgG should be antibody against spike protein, and reported as RBD, measured by [name] lab. We put alfa of 0.05 and beta of 0.2. The IgG positivity in JNJ-78436735 should be assumed as 80% and BNT162b2 as 60%.

6) Number of Subjects*

The Number needed in this study should be 93 per one arm, which is 186 in total. We assume 5-10% follow-up lost so we are going to enroll 200 patients in total.

For sub study to measure long term immunogenicity, we will enroll 50 patients among 200 participants.

The participants will be contacted via phone call in 6 months for monitoring.

7) Description of the study

This is the patient-blinded randomized controlled trial. To monitor patient reporting side effect properly, we are going to conduct the patient-blinded. Study team member will be aware after randomization, at the time of giving vaccination. This is not observer blinded. Also, to minimize bias, [name] lab members will not be notified which vaccine each participant receives. Randomization will be conducted via excel by [name]. Adult transplant recipients will be recruited from outpatient clinics. Transplant patients will be randomized in a 1:1 ratio.

8) Randomization of vaccine

A randomization schedule will be created using Microsoft Excel. [name] will randomly select 100 numbers out of 200 using excel. The selected number patients will receive JNJ-78436735 vaccine. The rest will receive BNT162b2 vaccine. Those randomized result will put into 200 envelopes. On top of each envelope, only study ID, from 001 to 200, will be written. The envelope will be filed in each patient's research chart. Charts will be located at the research office located at the Elliot Building. Only the study team will have access to the building.

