The sample size was based on previous studies, which had indicated a response rate of approximately 50% and 70% to each vaccine.

Therefore, for an alpha of 0.05 and a power of 80%, a sample size of 93 evaluable patients in each study group should be required. As we assume 10% of the patients will not be back, we have that margin and going to enroll 200 patients in total. The immunogenicity analysis will be only performed in those who received a vaccine dose and returned for follow-up serum (per-protocol population). The safety analysis will be performed in all patients who received the study vaccine regardless of whether they returned for follow-up serum. Demographics will be analyzed using descriptive statistics. Differences in vaccine response rates between the 2 arms will be compared using χ^2 test. Pre- and post-vaccination titers will be compared using Wilcoxon rank-sum test. Univariate analyses will be performed to determine significant factors affecting seroconversion using χ^2 test for categorical variables and Mann-Whitney U test for continuous variables. We will develop multivariate model to determine the factor of positive IgG post booster dosing. For multivariate analysis, a model should be developed using variables that had a P value < 0.2 on univariate analysis. Multivariate analysis will be performed using

IRB Study Number: 20210641
Version #4, Date: October 26, 2021

binary logistic regression. Statistical significance was defined as a P value < 0.05. Statistical analysis will be performed using IBM SPSS version 26.0.

15) Provisions to Monitor the Data to Ensure the Safety of Subjects*

Study Auditing and Monitoring

This study will be monitored (as applicable) and may be audited according to the University of Miami requirements. See also

<http://research.med.miami.edu/clinical-research/crors/monitoring>

Clinical Research Operations & Regulatory Support CRORS will provide internal study monitoring compliance. Following the monitoring plan, the monitors will verify that the clinical trial is conducted and data are generated and biological specimens are collected, documented (recorded), and reported in compliance with the protocol, International Conference on Harmonization Good Clinical Practice (ICH GCP), and applicable regulatory requirements.

Trial Monitoring, Auditing, and Inspecting

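### Enrolling 200 does not cover the stated 10% loss: 180 patients would be evaluable, 6 short of the required 186, though the effect on power is small

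*Combined protocol and SAP*

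**What the plan says.** The sample size is justified in two places in the combined protocol and SAP.

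- **Section 14 (Data Management), statistical paragraph.** The rates are taken from previous studies: "a response rate of approximately 50% and 70% to each vaccine". From these, "for an alpha of 0.05 and a power of 80%, a sample size of 93 evaluable patients in each study group should be required". The allowance for loss follows: "As we assume 10% of the patients will not be back, we have that margin and going to enroll 200 patients in total". The same paragraph limits the immunogenicity analysis to vaccinated patients who came back for the follow-up serum sample.
- **Sections 5 and 6 (Sample Size calculation; Number of Subjects).** Section 5 sets the error rates ("We put alfa of 0.05 and beta of 0.2") and a different pair of rates: "The IgG positivity in JNJ-78436735 should be assumed as 80% and BNT162b2 as 60" (percent). Section 6 gives the same 93 per arm and 186 in total, but a different loss: "We assume 5-10% follow-up lost so we are going to enroll 200 patients in total".

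Section 8 fixes the schedule at 200 envelopes, 100 per vaccine. No replacement of patients who fail to return is described.

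**The concern.** Three statements in section 14 cannot all be true: 186 evaluable patients are needed, 10% will be lost, and 200 enrolled provides the margin. The required number is described as evaluable, so it has not already been inflated for loss. Each patient who does not return leaves the primary analysis, so the loss comes straight off the primary sample.

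At stake is whether the plan delivers the 80% power it states for its primary endpoint. The two accounts also differ in both the loss figure and the response rates, so the reader cannot tell what power the plan stands behind once loss is allowed for.

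**Working it through.** **Inputs.** Required evaluable: 93 per arm, 186 in total (sections 6 and 14). Enrolled: 200, allocated 1:1 (sections 6 to 8). Loss: 10% (section 14) or 5–10% (section 6). Rates: 50% and 70% (section 14) or 60% and 80% (section 5). Alpha 0.05, power 80%. Test: chi-square on two proportions (section 14). Sidedness is not stated; two-sided is assumed because it reproduces the plan's figure.

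**1. Reproduce the 93.** With p̄ the mean of the two rates,

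n per arm = [1.960·√(2p̄(1−p̄)) + 0.842·√(p₁(1−p₁) + p₂(1−p₂))]² / (p₁−p₂)²

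- 50% versus 70%: (1.960 × 0.6928 + 0.842 × 0.6782)² / 0.04 = 92.999, so **93**. This matches the plan.
- 60% versus 80%: (1.960 × 0.6481 + 0.842 × 0.6325)² / 0.04 = 81.2, so **82**. This does not match.

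The stated requirement therefore belongs to section 14's rates, not section 5's.

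**2. Apply the loss to 200.**

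| Loss | Evaluable | Against 186 |
|---|---|---|
| 5% | 200 × 0.95 = 190 | 4 over |
| 7% | 200 × 0.93 = 186 | exact |
| 10% | 200 × 0.90 = 180 | 6 short |

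The largest loss covered is 1 − 186/200 = 7%. Meeting 186 at 10% loss needs 186/0.90 = 206.7, so 207 (208 for equal arms). Even the cruder 186 × 1.10 gives 205.

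If each patient independently has a 10% chance of not returning, the probability that at least 186 of 200 return is about 9%. With a 5% chance it is about 92%.

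**3. Power at the numbers that remain.** The normal approximation is

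power = Φ{[|p₁−p₂|·√n − 1.960·√(2p̄(1−p̄))] / √(p₁(1−p₁) + p₂(1−p₂))}

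The exact figures enumerate all outcomes of the uncorrected chi-square test. Equal loss in the two arms is assumed.

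| n per arm | 50% v 70%, approx. | 50% v 70%, exact | 60% v 80%, approx. | 60% v 80%, exact |
|---|---|---|---|---|
| 95 | 80.8% | 80.6% | – | – |
| 93 | 80.0% | 79.9% | 85.1% | 85.6% |
| 90 | 78.7% | 79.3% | 83.9% | 84.2% |
| 82 | – | – | 80.4% | 80.7% |

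Under 50% versus 70%, going from 93 to 90 per arm costs 80.0 − 78.7 = 1.3 points by approximation, or 79.9 − 79.3 = 0.6 points exactly.

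**4. The other pair of rates.** Under 60% versus 80%, 2 × 82 = 164 evaluable are enough for 80% power, and 200 covers a loss of 1 − 164/200 = 18%.

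**The case against.** The best case on the other side is that this is too small to matter. Power falls by 0.6 to 1.3 points, and the inputs are softer than the gap. Section 14 calls its rates approximate, and with the same formula 51% versus 70% would need 103 per arm, a change of 10 against a shortfall of 3. Section 6 gives loss as a range whose lower part is covered. Both accounts also state the same target (93 per arm) and the same nominal power, so the conflicting rates could be treated as a separate matter.

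Most of this stands as a limit on the size of the problem: the trial is not materially underpowered. It does not rescue the sentence, since at section 14's own loss figure the number left is 180, not 186. The shortfall against the stated 186 holds whichever rates apply; only the shortfall against 80% power depends on the pair. The rate conflict does deserve attention in its own right, but a correct replacement sentence cannot be written without choosing a pair.

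**Conclusion.** The concern holds. Against the plan's own requirement of 186 evaluable, 200 enrolled falls 6 short at 10% loss and suffices only up to 7%. Under 50% versus 70%, the pair that produces 93 per arm, power at 10% loss is about 79% instead of 80%. Under 60% versus 80% there is no shortfall in power.

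These results assume a two-sided test at 0.05, equal loss in the two arms and no replacement. The error is certain but its consequence is modest: it affects how the sample size is justified and does not threaten the trial's conclusion.

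**What to change.** Keep 200 and correct the text:

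1. Use a single loss figure in sections 6 and 14.
2. Use a single pair of response rates in sections 5 and 14, and state that the test is two-sided if that is the intention.
3. Replace the margin sentence. If 50% versus 70% is kept: *Enrolling 200 yields 186 evaluable patients if loss is 7%; at 10% loss, 180 (90 per arm) are evaluable and power is about 79%.* If 60% versus 80% is kept: *82 evaluable patients per arm are required; at 10% loss, 200 enrolled gives 90 per arm and power of about 84%.*

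This costs wording only. Enrolment, randomisation and analysis are unchanged, and under 50% versus 70% the plan states about 79% power at 10% loss instead of 80%.

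The alternative, if both 186 evaluable and 10% loss are to be kept, is to enrol 207, or 208 for equal arms. That means 7 or 8 more patients and an extension of the 200-envelope schedule in section 8. For a gain of about one point of power, the wording change is the proportionate choice.

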Already, there are several reports of increased immunogenicity with additional dosing of vaccination¹². Randomized controlled trial comparing placebo vs. other mRNA vaccine as a booster dose study showed some benefit¹³. However, as of now, there is no comparison study between mRNA and adenovirus vector vaccine. This time, we are conducting single center randomized controlled trial comparing mRNA vs. Adenovirus vector vaccine as a third dose after completion of two doses of mRNA vaccine in solid organ transplant recipients.

3) Inclusion and Exclusion Criteria*

Inclusion Criteria:

- *Patients 18 years of age and older*
- *Patients who had received a solid organ (kidney, liver, lung, heart, and pancreas) transplant patient from living or deceased donors.*
- *Patients with active graft with at least one immunosuppressive medication*
- *Completed two doses of BNT162b2 vaccination at least 28 days ago*

Exclusion Criteria:

- *Patient with non-active graft*
- *Any significant side effect with previous COVID-19 vaccination*
- *Within 28 days of BNT162b2 vaccine completion*
- *Already received more than and equal to three doses of COVID-19 vaccination*
- *Previously received COVID-19 vaccine other than BNT162b2 vaccine*
- *Previously received monoclonal Antibody treatment that are specifically directed against the spike protein for SARS-CoV-2 such as Mab, Bamlanivimab, etesevimab, Casirivimab, imdevimab, Sotrovimab and/or any combination.*

IRB Study Number: 20210641
 Version #4, Date: October 26, 2021

- *Thrombocytopenia (listed as a medical diagnosis or less than 50,000 per microliter 30 days prior vaccination)*
- *History of Capillary Leak Syndrome*
- *Adults unable to consent*
- *Individuals who are not yet adults (younger than 18 year old)*
- *Vulnerable patients (prisoners)*
- *Pregnant women*

4) Evaluation

Evaluation will be conducted as below schedule.

Procedures	Screening	Enrollment/Baseline Visit 1, Day 1	Phone Call Visit 2 48-96 hours	Phone Call Visit 3 6-8 days	Study Visit 4 Day 28 +/- 7 day	Study Visit 5 Month 6 (+/- 7 days)	Study Visit for Sub study only At Month 6 (+/- 30 days)
Informed consent	X	X					
Demographics	X	X					
Medical history	X	X					
Randomization	X	X					
Blood sample collection		X			X		X*
Vaccine Administration		X					
Symptom checker		X	X	X	X		
Phone call follow up			X	X	X	X	

* 50 optional participants only

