After obtaining consent, study team member, other than [name], will open the envelope to identify which vaccine to give. Each participant should be randomized and will receive one time dosing of either JNJ-78436735 or BNT162b2. After vaccination, those patients will need to stay Miami Transplant Institute outpatient clinic waiting area for 15minutes (+/- 2 minutes) to be monitored.

9) Discontinuation of patients:

- Patients may be discontinued under the following circumstances:
- A patient desire for discontinuation for any reason

IRB Study Number: 20210641
Version #4, Date: October 26, 2021

- Lost to follow up (every effort must be made to contact the patient)
- Death
- An Investigator's opinion that continuing the patient in the study is not appropriate

10) Study Timelines*

After consent is obtained, the blood draw for all patients will be done at the outpatient clinic phlebotomy room. After that, the participants will receive either vaccine. After vaccination, those patients will stay in the clinic for 15mins and if they have any symptoms, those patients will notify the research team. In the event of any severe reaction, the principal investigator will be notified immediately. Medical intervention will be address based on each case.

On visit 2, 48-96 hours after administration of the vaccine, the research team will call the patient to collect the side effect information. Again, visit 3, 6-8 days after enrollment, the research team will call the patient to collect side effect information. The participants will be back to the Miami Transplant Institute outpatient clinic in 28 (21-35) days from enrollment for follow-up blood collection. Upon follow up blood collection, the study team will ask the patient if they develop any symptoms after booster dosing.

We will also collect the blood test at 6 months (20-28 weeks) time period for those who are enrolled in the sub-study (50 patients will be enrolled)

11) Study Endpoints*

Primary endpoint is the anti-spike protein of SARS-CoV-2 virus IgG positive rate in one month after vaccination. Secondary endpoint includes the incidence rate of COVID-19 and the severity of COVID-19.

Safety endpoints includes side effect (i.e. pain at injection site, size of indwelling, fever, fatigue, and joint pain) at day 2 and 7 after vaccination. We also follow up to 6 months for any symptoms. This could also be gathered from the Jackson Health System medical record.

12) Procedures Involved*

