This is a single center single blinded (patient blinded) randomized controlled trial comparing BNT162b2 and JNJ-78436735vaccine as a third dose after completion of two doses of BNT162b2 vaccine in Solid Organ Transplant Recipients.

IRB Study Number: 20210641
Version #4, Date: October 26, 2021

Once informed consent is obtained, 10 ml of blood from the participants will be obtained at day 0 and day 28(21-35) to monitor IgG and IgM against SARS-CoV-2 spike protein. Then, a Jackson transplant nurse and/or medical assistant will intramuscularly inject either vaccine to the participants. The source of clinical information will be collected through Jackson Health System electronical medical record.

Blood test will be analyzed [name] lab in University of Miami.

As an optional sub study for 50 participants, we will collect 10 ml of blood again at 6months (20-28 weeks) time to monitor IgG and IgM.

After vaccination, those patients will need to stay Miami Transplant Institute outpatient clinic waiting area for 15minutes (+/- 2 minutes) to be monitored.

Unblinding Process:

The vaccine given at the time of enrollment will be unblinded upon patient's request at Day 28. However, if an emergency, the vaccine will be unblinded immediately for the patient.

A potential early unblinding event could occur if the patient's healthcare provider, including Jackson, provides the vaccine records from Florida Shot.

However, the early unblinding event should only affect the study secondary outcomes and will not affect primary outcome, i.e. serology data.

13) Data and Specimen Banking*

Blood specimen will be stored in [name] lab for 5 years. For sub-study, we will also obtain PBMC and this should also be stored in 5 years. Only the research team member will have an access to those specimen.

For clinical data, we will use a unique ID for each patient that does not include or derive from any identifiers. Miami Transplant Institute will retain the key to these IDs subject to local IRB review.

14) Data Management*

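### The primary chi-square on Day 28 IgG positivity is valid, but it leaves out the Day 1 IgG measured on every patient; a test stratified by Day 1 IgG would be modestly more powerful at almost no cost

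*Combined protocol and SAP*

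**What the plan says.** The endpoint in section 11 is Day 28 status alone: "Primary endpoint is the anti-spike protein of SARS-CoV-2 virus IgG positive rate in one month after vaccination". In the statistical text of section 14, "Differences in vaccine response rates between the 2 arms will be compared using" a chi-square test; no stratum or covariate is named.

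A baseline value exists for everyone. Section 4 states: "Blood samples will be obtained from all patients at the time of enrollment (Day 1) and day 28 to test IgG and IgM". Sections 10 and 12 both place the draw ahead of the injection; section 10 describes the draw and continues "After that, the participants will receive either vaccine".

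Nothing in section 3 depends on antibody status. The vaccine-history criterion is "Completed two doses of BNT162b2 vaccination at least 28 days ago". The immunogenicity population in section 14 is defined only by receiving the dose and returning for serum. Allocation in section 8 is a simple draw of 100 numbers out of 200, so Day 1 IgG is not balanced by design either.

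Section 14 has two other places where baseline IgG appears or could appear. One is a pre/post titer comparison. The other is a factor-finding logistic model whose variables enter on univariate P < 0.2; Day 1 IgG is not named there. Neither is a pre-specified comparison of the arms adjusted for Day 1 IgG.

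**The concern.** A patient who is IgG-positive on Day 1 and still positive on Day 28 says little about which booster works better. In an unadjusted test such patients still add to the variance of each arm's positive rate. If Day 1 status predicts Day 28 status, comparing the arms within Day 1 strata removes that part of the variance. The patients and the target quantity stay the same.

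Interpretation is also at stake. The overall Day 28 rate mixes positivity that arose after the booster with positivity already present. No planned arm comparison separates the two.

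**Working it through.** **The plan's own figure.** Inputs from section 14: 50% and 70%, alpha 0.05, power 80%. Sidedness is not stated; two-sided reproduces the result. With the pooled-variance formula,

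n = [1.960·√(2·0.6·0.4) + 0.8416·√(0.5·0.5 + 0.7·0.3)]² / 0.20² = (1.358 + 0.571)² / 0.04 = 93 per arm.

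This matches the plan. Section 5 gives different rates: "The IgG positivity in JNJ-78436735 should be assumed as 80% and BNT162b2 as 60"%. At 60/80 the same formula needs 82, and 93 per arm gives 85% power by formula (86% by simulation). Both pairs are carried below.

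**Assumptions.** Let b be the share IgG-positive on Day 1 and s the chance that such a patient is positive on Day 28, equal in both arms. Neither is in the documents. The overall Day 28 rates are held at the plan's values, so the rate in Day 1 negatives is (overall − b·s)/(1 − b), and the difference in negatives is 0.20/(1 − b), that is 22, 25 or 29 points at b = 10, 20 or 30%. At 50/70:
- b = 0.1, s = 0.80: (0.50 − 0.08)/0.9 = 47% against (0.70 − 0.08)/0.9 = 69%.
- b = 0.3, s = 0.95: (0.50 − 0.285)/0.7 = 31% against (0.70 − 0.285)/0.7 = 59%.

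**Power.** Simulated, 400,000 trials per scenario, 93 per arm, two-sided 5%, uncorrected CMH stratified by Day 1 IgG:

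| Overall rates | Plain chi-square | s | CMH, b = 10% | b = 20% | b = 30% |
|---|---|---|---|---|---|
| 50/70 | 0.799 | 0.80 | 0.809 | 0.818 | 0.830 |
| 50/70 | 0.799 | 0.90 | 0.818 | 0.838 | 0.865 |
| 50/70 | 0.799 | 0.95 | 0.824 | 0.852 | 0.889 |
| 60/80 | 0.856 | 0.80 | 0.857 | 0.858 | 0.860 |
| 60/80 | 0.856 | 0.90 | 0.862 | 0.869 | 0.881 |
| 60/80 | 0.856 | 0.95 | 0.865 | 0.879 | 0.897 |

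Repeat simulations agree to within about 0.2 points. To match these CMH powers, the plain test would need 96 to 121 per arm at 50/70, or 94 to 106 at 60/80.

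**Hand check at 50/70.** The pooled variance of the plain test is 0.6·0.4 = 0.24. The within-stratum variance is (1 − b)·m(1 − m) + b·s(1 − s), where m is the mean rate in negatives.
- b = 0.1, s = 0.80: m = 0.578, variance 0.2356, 93·0.24/0.2356 ≈ 95 (simulated 96).
- b = 0.2, s = 0.90: m = 0.525, variance 0.2175, 93·0.24/0.2175 ≈ 103 (simulated 104).
- b = 0.3, s = 0.95: m = 0.450, variance 0.1875, 93·0.24/0.1875 ≈ 119 (simulated 121).

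**Validity.** Under no difference the type I error is 0.047 to 0.052 for the plain test and 0.049 to 0.051 for CMH. The Mantel-Haenszel risk difference averages 0.2005 to 0.2013 against a true 0.200, and its 95% interval covers 94.7 to 95.0%.

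**Downside.** If Day 1 IgG is uninformative, CMH loses 0.2 points (50/70) to 0.5 points (60/80). With 5% of Day 1 results unknown and kept as a third stratum, it loses at most about 0.6 points.

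**If 50/70 describes Day 1 negatives only.** Over shares of 10 to 40%, stratifying gains 2 to 9 points if all positives persist and 1 to 4 if 90% do. Power still stays below 80% (76 to 58%, or 74 to 49%).

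**The case against.** The strongest reply is that nothing here is broken. An unadjusted chi-square is an accepted primary test for a binary endpoint in a 1:1 trial, and it meets the target at the planned evaluable number. The gain rests on two figures that the documents do not give. In 12 of the 18 scenarios above it is 2.5 points or less, and the 9 points come from the single most favourable one. All of this stands, and it is why the point is an efficiency suggestion.

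A second reply concerns the software. A continuity-corrected CMH has lower power than the plain chi-square in 14 of the 18 scenarios, and not only when few patients are positive on Day 1. With a 30% share and 80% persistence it gives 0.786 against 0.799 at 50/70, and 0.819 against 0.856 at 60/80. Its type I error is 0.026 to 0.035. The plan names SPSS 26.0, and the documents do not show which version of the statistic would be reported. This also stands: the uncorrected statistic has to be named.

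Third, study staff know the allocation (section 7), so a change of primary test is credible only if made before outcomes by arm are seen. That is a condition on the fix and does not count against it.

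On the other side, the plan has little slack. At its own 10% loss, 200 enrolled leaves 90 per arm, and plain power at 50/70 is 78.7% by formula (79.3% simulated). At 90 per arm CMH gives 79.6% (b = 10%, s = 80%), 80.6% (10%, 90%), 82.7% (20%, 90%) and 87.8% (30%, 95%).

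**Conclusion.** The point holds as an efficiency improvement. The primary chi-square is valid and unbiased and delivers 80% power at 50/70 with 93 evaluable per arm, but it ignores an informative baseline value already collected on every patient. For assumed Day 1 positive shares of 10 to 30% and persistence of 80 to 95%, stratifying adds about 1 to 9 points of power at 50/70 and about 0 to 4 at 60/80. The worst case, an uninformative baseline, costs half a point or less.

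Larger gains need near-perfect persistence and are not relied on. For example, a 40% share with all staying positive implies 17% against 50% in Day 1 negatives at 50/70, which nothing in the documents supports. Both tests assume that loss to follow-up serum does not differ between arms. The conflict between the two pairs of planning rates changes the size of the gain but not the recommendation.

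**What to change.** Pre-specify in section 14, before any outcome data by arm are seen:

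- **Primary test:** Cochran-Mantel-Haenszel without continuity correction, stratified by Day 1 IgG (positive, negative, unknown), so that no patient is dropped.
- **Estimate:** Mantel-Haenszel risk difference with 95% confidence interval.
- **Sensitivity analysis:** the plain chi-square as now written.
- **Supporting analysis:** Day 28 IgG positivity by arm among Day 1 IgG-negative patients.

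The cost is analysis-plan wording; no sample, visit or patient is added. The text must state that the statistic is uncorrected. If the named software does not report that version, the test and the risk difference can be computed directly from the 2×2 table in each stratum.

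### Pre- and post-vaccination titers are paired within patient, but the plan names the Wilcoxon rank-sum test, which assumes independent samples, and does not say whether arms are pooled

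*Combined protocol and SAP*

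**What the plan says.** The titer analysis is one sentence in the statistical paragraph of Section 14 (Data Management): "Pre- and post-vaccination titers will be compared using Wilcoxon rank-sum test". The sentence before it concerns response rates and does name the arms: "Differences in vaccine response rates between the 2 arms will be compared", by chi-square. The sentence after it, on factors affecting seroconversion, uses the "Mann-Whitney U test for continuous variables".

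The sampling scheme appears twice. Section 4 (Evaluation): "Blood samples will be obtained from all patients at the time of enrollment (Day 1) and day 28". Section 12 (Procedures Involved): "10 ml of blood from the participants will be obtained at day 0 and day 28(21-35" days), with the first draw taken before the injection. The analysis set is defined in Section 14: "The immunogenicity analysis will be only performed in those who received a vaccine dose and returned for follow-up serum".

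Section 11 (Study Endpoints) lists no titer endpoint: "Primary endpoint is the anti-spike protein of SARS-CoV-2 virus IgG positive rate in one month after vaccination". No section names a paired method.

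**The concern.** The sentence sets pre against post, and both values come from the same person. The rank-sum test takes its null variance from two independent samples. It is the Mann-Whitney U test under another name, which the plan itself uses one sentence later for unpaired groups. With paired data that variance is wrong. If a patient's two titers are positively correlated, p-values are too large and a modest real rise may be reported as non-significant. If they were negatively correlated, the test would reject too often.

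The sentence also leaves open whether the comparison is made in each arm or in both arms together. These are different analyses with different numbers of pairs.

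This is the only planned analysis of titers and the only one that explicitly sets baseline serum against day 28 serum. Section 3 does not exclude patients who are already IgG-positive at entry, so day 28 positivity alone does not show what the booster added.

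**Working it through.** **Inputs from the documents.** Two samples per patient (Sections 4 and 12); analysis in those with follow-up serum (Section 14); significance at P < 0.05 (Section 14), taken as two-sided; 93 evaluable patients per arm, 186 in total (Sections 6 and 14).

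**Inputs assumed.** The documents give no pre/post correlation, no titer shift and no statement on pooling. I take log titers as bivariate normal with equal variances, correlation ρ of 0.3, 0.5 and 0.7, and a shift d of 0.2 to 0.8 SD. The number of pairs n is 93 (per arm) or 186 (pooled).

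**The plan's own figure.** "The Number needed in this study should be 93 per one arm, which is 186 in total" rests on the binary endpoint. With the 50% and 70% response rates of Section 14:

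n = [1.96·√(2·0.6·0.4) + 0.842·√(0.5·0.5 + 0.7·0.3)]² / 0.2² = [1.358 + 0.571]² / 0.04 ≈ 93.

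The figure reproduces and does not involve titers.

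**Size of rank-sum on paired data.** Under the null, the rank-sum z has variance of about 1 − ρ_s, where ρ_s = (6/π)·arcsin(ρ/2). True two-sided size = 2·[1 − Φ(1.96/√(1 − ρ_s))]. The simulation used 40,000 replicates.

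| ρ | ρ_s | √(1 − ρ_s) | Size, formula | Rank-sum simulated, 93 / 186 pairs | Signed-rank simulated, 93 / 186 pairs |
|---|---|---|---|---|---|
| −0.3 | −0.288 | 1.135 | 8.4% | 8.4% / 8.5% | 5.0% / 5.1% |
| 0 | 0 | 1 | 5.0% | 5.0% / 4.8% | 5.0% / 4.9% |
| 0.3 | 0.288 | 0.844 | 2.0% | 2.1% / 2.0% | 5.0% / 5.0% |
| 0.5 | 0.483 | 0.719 | 0.6% | 0.6% / 0.8% | 4.9% / 5.2% |
| 0.7 | 0.683 | 0.563 | 0.05% | 0.07% / 0.06% | 5.1% / 5.0% |

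The distortion depends on ρ and hardly at all on the number of pairs.

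**Power, one case by hand** (n = 93, ρ = 0.5, d = 0.3; rank-test efficiency 3/π = 0.955):

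- Rank-sum: mean z = 0.3·√(93/2)·√0.955 = 2.00, with SD 0.719. Power = Φ((2.00 − 1.96)/0.719) ≈ 52%.
- Signed-rank: mean z = 0.3·√93·√0.955/√(2·(1 − 0.5)) = 2.83. Power = Φ(2.83 − 1.96) ≈ 81%.

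**Power by simulation** (20,000 replicates; ρ = 0.3 / 0.5 / 0.7):

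| Pairs | Rise | Rank-sum (%) | Signed-rank (%) |
|---|---|---|---|
| 93 | 0.2 SD | 22.2 / 19.0 / 13.6 | 34.5 / 46.0 / 66.9 |
| 93 | 0.3 SD | 50.9 / 51.6 / 52.0 | 65.3 / 80.3 / 95.1 |
| 93 | 0.5 SD | 94.6 / 97.0 / 99.1 | 97.6 / 99.6 / 100 |
| 186 | 0.2 SD | 46.0 / 45.2 / 45.0 | 61.1 / 75.4 / 93.1 |
| 186 | 0.3 SD | 84.1 / 88.4 / 93.3 | 91.8 / 97.9 / 99.9 |
| 186 | 0.5 SD | 99.9 / 100 / 100 | 100 / 100 / 100 |

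At 0.8 SD both tests reach 100% for either number of pairs. A separate simulation with 4,000 runs per setting gave the same picture: for 93 pairs and ρ = 0.5, size 0.7% against 4.8%, and power at 0.3 SD of 52% against 80%.

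**Values at an assay floor.** As a sensitivity check, 20% or 50% of day 28 values were set to a common floor. Reading the plan's 50-80% positivity as a floor proportion is itself an assumption, because a negative result need not be a floor value. The size of rank-sum at 93 pairs was 2.3 / 0.8 / 0.1% with 20% at the floor and 2.6 / 1.2 / 0.2% with 50%. At 0.3 SD with 50% at the floor, power was 41.5 / 40.1 / 37.5% against 49.0 / 59.3 / 77.0%.

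**The case against.** The sentence follows directly on one about the two arms. It can be read as carrying that over, with pre titers and post titers each compared between arms. Rank-sum is then valid. This reading cannot be ruled out, so the error is conditional; that the sentence fails to say which comparison it means is not. The wording sets pre against post and drops the reference to arms that its neighbor includes, so the within-patient reading remains the more natural one. Rank-sum may be a slip for signed-rank, but that is inference.

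The consequences are also limited. Titers are not a listed endpoint, the trial's hypothesis is between arms, and no sample size or decision rule uses this test. With positive correlation the error costs power and does not create false claims. Nothing in the documents suggests a negative correlation, so the 8.4-8.5% figure shows only the direction of the error.

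Finally, the large losses occur only for rises of 0.2-0.3 SD, and nothing in the documents points to a rise that small. At 0.5 SD with 93 pairs the loss is at most about 3 points, and at 0.8 SD it is nil. All of this stands. It limits the weight of the point but does not make the named test right for paired titers.

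**Conclusion.** The concern holds. On the within-patient reading, the plan prescribes an independent-samples test for paired data and so gives wrong p-values. On the between-arm reading the test is sound, but the sentence does not state that comparison. Either way it needs correcting.

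The loss ranges from nil for a large titer rise to more than 50 percentage points of power for a small rise with high correlation (93 pairs, 0.2 SD, ρ = 0.7: 66.9 − 13.6 = 53.3). Correlation, shift, pooling and the normal model are assumptions, and the documents do not show where in this range the trial would fall. The effect is confined to the titer comparison. The point should be corrected before analysis, but it does not threaten the primary result.

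**What to change.** Replace the sentence with wording such as: *Within-patient change from pre- to post-vaccination titer will be tested with the Wilcoxon signed-rank test (paired).* Add whether this is done within each arm or in both arms pooled. If titers are also to be compared between arms, say so in a separate sentence and keep the rank-sum (Mann-Whitney) test for that comparison only.

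The cost is one or two sentences. Data collection, sample size and the primary analysis do not change. Section 27 restricts departures from the protocol without a formal amendment, so it is better to correct the text before analysis than to leave the analyst to substitute a test without a record.
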